#### 4.5.3 Safety Parameters

Five safety events of interests are defined by the laboratory data measured every month and the blood pressure measured at every dialysis session: potassium, phosphorus, bicarbonate, albumin and post-dialytic systolic blood pressure. For monitoring by the DSMB, the thresholds for defining each safety event were determined based on the distribution of the in the Usual Care arm for laboratory measures, and based on clinical significance for post-dialysis blood pressure. The five safety events are (1) hypokalemia defined as potassium < 3.6 mEq/L; (2) hypophosphatemia defined as phosphorus < 3.0 mg/dL; (3) hyperbicarbonatemia defined bicarbonate > 26 mEq/L; (4) hypoalbuminemia defined as albumin < 3.2 g/dL; and (5) hypotension defined as post-dialytic systolic blood pressure < 90 mmHg. The safety events are summarized as events per 100 participant-years. The difference in event rates between treatment arms will be compared using the GEE models as previously described.

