#### 4.5 Secondary Outcomes

Secondary outcomes include hospitalization rates using data collected during the follow-up period, pre- and post-dialysis blood pressure using data from each dialysis session, and ultra-filtration rate calculated using data from each dialysis session, laboratory data measured every month, and quality of life measured approximately annually. Analyses of the secondary outcomes will be performed for the primary analysis population (Watson V  $\leq$ 42.5L), for the extended analysis population (all participants regardless of Watson V), and for the subgroup of participants with Watson V >42.5L, as well as in the stratified analyses.

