#### 4.5.4 Blood pressure

The pre- and post-dialysis blood pressures during each dialysis session will be summarized by the weighted average to account for the unequal number of dialysis sessions per participant. The differences in overall mean and slope over the study period between treatment arms will be compared using linear mixed effects models to account for both participants within the same facility and repeated measurements within the same participant.

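### Monthly laboratory data are a secondary outcome in the SAP, yet the only between-arm laboratory analysis is four one-sided safety-event rates; adding the mixed model already planned for blood pressure would be a cheap gain in sensitivity.

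*Combined protocol and SAP*

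**What the plan says.** SAP 4.5 (Secondary Outcomes) includes in its list "laboratory data measured every month, and quality of life measured approximately annually". It names no analyte. It commits the secondary outcomes to analysis in the primary population, the extended population and the subgroup above 42.5 L. Protocol 4.7.2 and the outcome list in SAP 1 contain no laboratory outcome.

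SAP 4.5.3 (Safety Parameters) is the only place that gives a between-arm method for a laboratory value. It begins: "Five safety events of interests are defined by the laboratory data measured every month and the blood pressure measured at every dialysis session". The four laboratory events are "hypokalemia defined as potassium < 3.6 mEq/L", "hypophosphatemia defined as phosphorus < 3.0 mg/dL", "hyperbicarbonatemia defined bicarbonate > 26 mEq/L" and "hypoalbuminemia defined as albumin < 3.2 g/dL". Each looks at one side only. The section ties the cut-offs to DSMB monitoring and says that the "thresholds for defining each safety event were determined based on the distribution of the in the Usual Care arm for laboratory measures"; the blood pressure cut-off is said to rest on clinical significance. It does not state which percentile was used. Events are expressed per 100 participant-years and compared with the GEE approach given for hospitalizations. The section does not say whether every monthly value beyond the cut-off counts or only the first.

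Blood pressure is also analysed on its full scale in SAP 4.5.4: "The differences in overall mean and slope over the study period between treatment arms will be compared using linear mixed effects models". SAP 4.5.5 does the same for ultrafiltration rate. No such model is written for the laboratory measures.

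**The concern.** Post-dialysis systolic pressure is handled in two complementary ways, as a threshold event and as a continuous measure. The four laboratory measures are handled only in the first way, and the SAP gives no reason for the difference. The listed laboratory outcome therefore has no analysis of level or trend.

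This matters for two reasons. First, Protocol 4.7.2.2 expects longer sessions to increase solute clearance, which for dialysed solutes suggests movement of the whole distribution. A one-sided count uses only part of that information, and it misses change confined to the other end, such as fewer high phosphorus values. Second, Protocol 7.1 states that adverse events will not be collected. Apart from death, hospitalization and blood pressure, these comparisons are most of what the trial can say about tolerability. A finding of no difference in event rates could be read as no laboratory effect when a modest shift in the mean had occurred.

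**Working it through.** The documents give no power, SD, within-participant correlation or tail share for any laboratory measure, so there is no plan figure to reproduce. As a check of method on a nearby continuous outcome, take the quality-of-life figure in Protocol 6.2: 4020 × 50% / 2 = 1005 per arm, SD 10, and design effect 1 + 9 × 0.03 = 1.27. The detectable difference is 2.80 × 10 × √(2 × 1.27/1005) = 1.41, against 1.4 stated.

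**Inputs from the documents:** two-sided 0.05; 1:1 allocation of facilities; monthly laboratory values (Protocol 4.8); 4250 participants in the primary population and 256 facilities (Protocol 6.2.1).

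**Assumed inputs:** normal values; a uniform shift; share beyond the cut-off p = 5%, 10% or 25%; within-participant correlation ρ = 0.3, 0.5 or 0.7; m = 24 monthly values (the median follow-up of 2.5 years would allow about 30); every value beyond the cut-off counted; facility clustering affecting both analyses equally.

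**Relative efficiency of the count against the participant mean**

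- Variance of the participant mean, in SD² of a single value: Vm = ρ + (1−ρ)/m.
- Variance of the participant's proportion beyond the cut-off: Vc = p(1−p)/m + ((m−1)/m) × [Φ₂(c,c;ρ) − p²], where c is the normal quantile of p.
- Efficiency E = φ(c)² × Vm / Vc.
- Power where the mean has 80%: Φ(2.80 × √E − 1.96).

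Least favourable corner, p = 5% and ρ = 0.7: φ(c) = 0.1031, Φ₂ = 0.0196, Vm = 0.7125, Vc = 0.0475/24 + (23/24) × (0.0196 − 0.0025) = 0.0184. E = 0.0106 × 0.7125/0.0184 = 0.41, and power is 44%.

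Most favourable corner, p = 25% and ρ = 0.3: φ(c) = 0.3178, Φ₂ = 0.0951, Vm = 0.3292, Vc = 0.1875/24 + (23/24) × (0.0951 − 0.0625) = 0.0391. E = 0.85, and power is 73%.

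| Share beyond cut-off | ρ = 0.3 | ρ = 0.5 | ρ = 0.7 |
|---|---|---|---|
| 5% | 54% | 50% | 44% |
| 10% | 64% | 61% | 56% |
| 25% | 73% | 72% | 70% |

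The loss is 7 to 36 points. Simulating the two corners with a log-rate test and robust variance gave 43% and 73%, with the mean at about 80%.

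**Sensitivity of the loss to the assumed inputs**

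- 12 monthly values, same p and ρ: about 10 to 38 points.
- Cut-off at the 2.5% tail (m = 24): 36 to 47 points.
- Cut-off at the median (m = 24): 3 to 5 points.
- First event only, simulated (m = 24): about 3 to 28 points.
- One value per participant: 26 points (p = 25%) to 54 points (p = 5%).

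Under a uniform normal shift the count lost power in every case tried.

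**Size of the shift involved.** With 4250/2 = 2125 per arm, 4250/256 = 16.6 per facility, equal facility sizes and an assumed ICC of 0.03, the design effect is 1 + 15.6 × 0.03 = 1.47. The shift that the mean detects with 80% power is 2.80 × √(2 × 1.47 × Vm/2125), which is 0.060 SD for ρ = 0.3 and 0.088 SD for ρ = 0.7. Dividing by √E gives the count's 80% point: 0.060/√0.85 = 0.065 SD to 0.088/√0.41 = 0.137 SD. At 0.15 SD the count has 87% power or more across these scenarios, and at 0.20 SD at least 98%. With ICC 0.05 the worst corner is 80% at 0.15 SD and 96% at 0.20 SD.

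**The case against.** The best defence is that these are safety events and do what safety events should do. Harm from low potassium, low phosphorus, high bicarbonate or low albumin lies in the extremes, so the rate of extreme values is a proper target. The uniform-shift model favours the mean by construction, and an effect confined to the tail could favour the count. The trial is also large enough for the count to find anything but a small shift. All of this stands. It is why the event comparison should stay and why the severity is low.

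Three stronger readings are tempting, and the documents do not support them. A reader might infer that the four analytes are themselves named as secondary outcomes. SAP 4.5 names only laboratory data as a group, and the four appear by name as safety events. A reader might take 7 to 36 points as the power this plan gives up. None of the inputs behind that range is in the documents, and SAP 4.5.3 leaves open whether repeat events count, which changes the answer. A reader might also conclude that the mean comparison should replace the event comparison. That would weaken protection against harm in the tail, which is the stated purpose of the section.

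The defence does not explain why a listed secondary outcome has no full-scale analysis when blood pressure, in the same part of the SAP, has both.

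**Conclusion.** The point holds as a modest gap. Monthly laboratory data are a listed secondary outcome in the SAP, and their only specified comparison is a set of one-sided event rates that are less sensitive to a general shift and do not register change confined to the opposite tail. The direction of the loss is secure for a uniform normal shift. Its size is illustrative: about 44-73% power against 80% under the assumed tail shares, correlation and number of values, and losses from about 3 to over 50 points under other choices. At the planned size, with an assumed ICC of 0.03 and the same illustrative inputs, the material loss is confined to shifts of roughly 0.14 SD or less, and the documents do not say whether shifts that small matter. The validity of the safety-event comparison is not in question. This is a cheap improvement of low severity.

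**What to change.** Keep the safety-event rates and their GEE comparison in SAP 4.5.3 as the safety analysis, and state there whether repeated monthly values count as separate events. Add to SAP 4.5 the linear mixed model of 4.5.4 for monthly potassium, phosphorus, bicarbonate and albumin: overall mean and slope by arm, with facility and participant random effects. Report each mean difference beside the matching event-rate difference.

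Do not adjust for the first available value unless it is a defined entry value that precedes the intervention. Facilities are assigned before patients enrol (Protocol 5.3.1) and the recommendation applies to patients starting dialysis (Protocol 4.5), so a first recorded value may already reflect the assigned approach.

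The cost is SAP wording and four further fits of a model form that the SAP already specifies; no new data are needed. The downside is four more secondary estimates, which need the event rates beside them for clinical reading.

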#### Laboratory Data: once per month

In alignment with usual practice, the following laboratory test results will be made available to the DCC by electronic data transfer once per month. It is expected that periodically some lab results will be missing and that repeated lab values will be present.

- 1. Pre-dialysis blood urea nitrogen
- 2. Post-dialysis blood urea nitrogen
- 3. Hemoglobin
- 4. White blood count
- 5. Albumin
- 6. Creatinine
- 7. Sodium
- 8. Potassium
- 9. Bicarbonate
- 10. Chloride
- 11. Calcium
- 12. Phosphorus
- 13. Glucose

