A major objective of the trial is to evaluate effectiveness of the intervention for the overall population of patients receiving maintenance hemodialysis rather than to evaluate efficacy of the intervention for a selected, non-representative subset. Because the randomized treatment assignment for the dialysis facility will be determined before patients are enrolled, a requirement for patient-level informed consent would likely result in important differences in the characteristics of participants in the two treatment groups (intervention patients would be those who *a priori* are interested in having longer dialysis sessions and the usual care cohort would be "all comers"). These differences would substantially undermine the objectives of the TiME Trial.

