#### Intent-to-Treat Analysis of Mortality

The primary outcome is time to death and the primary analyses will include participants in the primary treatment assessment population only. The primary and main secondary analyses of treatment effectiveness will be intention-to-treat, i.e., each participant will be included in the group in which her/his dialysis facility was randomized, regardless of adherence to the assigned strategy. The primary analysis will be performed using Cox proportional hazards model to compare the survival rates between the Intervention and usual care arms stratified by the stratification variables (see section 4.4). Variance estimation will be calculated by the robust variance estimator to adjust for clustering by facility. In secondary analyses of mortality, time by treatment interaction terms will be applied to determine whether the treatment effect on mortality varies as a function of the amount of time the patient has been on the intervention. In addition, treatment by body size and treatment by sex interaction terms will be considered to assess whether treatment effects differ by body size or gender subgroups. Multivariable Cox regression will also be used to assess the sensitivity of the results to adjustment for baseline patient and center characteristics that are not balanced between the two treatment arms and that are predictive of the death outcome.

In additional secondary analyses of mortality, each of the above analyses will be performed in the extended population including all participants in the study, as well as in the large-size subgroup of patients >42.5 L to address any indirect effects of the intervention.

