#### 4.5.1 Hospitalizations

Hospitalization data will be analyzed in two ways. First, time to the first hospitalization will be compared between treatment groups using multivariable Cox proportional hazards models adjusting for clustering. Second, to compare the hospitalization rates between treatment groups, a generalized estimating equations (GEE) approach will be used assuming a Poisson distribution with an offset term to account for the length of follow-up for each participant and an independent correlation structure to account for participants within the same facility. Similar to the analyses of the primary endpoint, analyses will be performed for the primary treatment assessment population and the extended analysis population.

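### The laboratory safety rate ratios in SAP 4.5.3 use no entry value; if repeated monthly events are counted, an entry-adjusted ratio reported beside them would be more precise

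*Combined protocol and SAP*

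**What the plan says.** SAP 4.5.3 defines four laboratory safety events: potassium below 3.6 mEq/L, phosphorus below 3.0 mg/dL, bicarbonate above 26 mEq/L and albumin below 3.2 g/dL. A fifth event, low post-dialysis systolic pressure, is not a laboratory measure and is outside this point. For DSMB monitoring, "the thresholds for defining each safety event were determined based on the distribution of the in the Usual Care arm for laboratory measures". Events are summarized per 100 participant-years, and "The difference in event rates between treatment arms will be compared using the GEE models as previously described".

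The only GEE the SAP describes before that is the hospitalization model of 4.5.1, fitted "assuming a Poisson distribution with an offset term to account for the length of follow-up for each participant", with an independence working structure within facility. It names no covariate.

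No other section supplies an entry laboratory value:

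- The study-entry data list in protocol 4.8 contains none.
- The only baseline window in the SAP (4.5.2) is for the KDQOL.
- SAP 4.2 describes baseline balance but adjusts nothing.
- The multivariable linear model in SAP 4.1 names no covariates.

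For mortality, protocol 6.3 does plan an adjusted companion: "Multivariable Cox regression will also be used to assess the sensitivity of the results to adjustment for baseline patient and center characteristics" where these are unbalanced and predictive of death.

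On the data, protocol 4.8 says "the following laboratory test results will be made available to the DCC by electronic data transfer once per month" and adds: "It is expected that periodically some lab results will be missing". SAP 4.5 lists "laboratory data measured every month, and quality of life measured approximately annually" among the secondary outcomes, but only 4.5.3 states a between-arm model for laboratory data.

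**The concern.** Participants enter within 120 days of starting dialysis and there is no laboratory criterion, so some may already be beyond a cut-off at entry. Monthly values from one patient are correlated. A patient who starts low therefore tends to contribute many events in either arm, and that between-patient spread goes into the standard error of the arm comparison. An entry value would explain part of it.

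What is at stake is the chance of seeing a modest excess. Protocol 7.1 collects no adverse events as such; it relies on serious technical complications appearing as hospitalizations or deaths. In these documents SAP 4.5.3 is the only laboratory comparison between arms with a stated model. Protocol 1.1 expects longer sessions to increase solute removal, so more low potassium or phosphorus values are a plausible direction of harm. A wider interval makes such an excess easier to miss.

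**Working it through.** **No stated figure to reproduce.** The documents give no laboratory event rate, standard error or power for this comparison, so its size has to be simulated under stated assumptions.

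**Models compared.** For participant i with event count Y and follow-up T:

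- Planned: log E(Y) = a + b·arm + log T
- With entry value: log E(Y) = a + b·arm + c·(entry value) + log T

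Both are Poisson with independence working correlation and robust variance by facility. The measure is SE(b) with the entry term divided by SE(b) without it.

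**Inputs from the documents.** 256 facilities, 6,880 patients (4,250 in the primary analysis population), cluster-size SD 10 or 16, enrollment over 36 of 54 months, 18% deaths and 10% losses per year (protocol 6.2.1), allocation 1:1 (4.4), follow-up up to 3 years (4.9).

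**Inputs assumed, because the documents give none.** Within-patient correlation, its fading over time, the share of values beyond the cut-off, the facility ICC of laboratory values, and the size of any effect.

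**Set A.** 6,880 patients, facility-size SD about 16, laboratory ICC 0.02, every monthly value counted. SE ratio at 5% / 13% / 30% of values beyond the cut-off:

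| Early correlation | Halves every 6 months | Halves every 12 months | Never fades |
|---|---|---|---|
| 0.3 | 0.929 / 0.920 / 0.915 | 0.897 / 0.883 / 0.876 | 0.815 / 0.790 / 0.774 |
| 0.5 | 0.901 / 0.885 / 0.876 | 0.855 / 0.830 / 0.817 | 0.739 / 0.693 / 0.662 |
| 0.7 | 0.879 / 0.856 / 0.842 | 0.826 / 0.791 / 0.769 | 0.741 / 0.673 / 0.614 |

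With fading, the cut runs from 1 - 0.929 = 7% to 1 - 0.769 = 23%. Without fading it runs from 1 - 0.815 = 18% to 1 - 0.614 = 39%.

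**Set B.** 4,250 patients, facility-size SD 10, monthly event probability 3-20%, entry-to-later correlation 0.2-0.6, ICC 0.01-0.05, linear and quadratic entry terms. The standard error fell in all 24 settings with every event counted, by 5% (0.0707 to 0.0669) to 43% (0.0600 to 0.0341). With the entry value drawn before any effect, the rate ratio was 1.185 with and without the term (300 replicates).

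**Both population sizes.** A further check gave SE ratios of about 0.60-0.93 at 6,880 patients and 0.65-0.94 at 4,250.

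**What this does to an interval.** Take an illustrative ratio of 1.10 (log 0.0953) and two Set B settings (10% events, ICC 0.01):

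- Entry correlation 0.5: SE 0.0572 gives exp(0.0953 ± 0.1121) = 0.98 to 1.23. SE 0.0423 gives exp(0.0953 ± 0.0829) = 1.01 to 1.20.
- Entry correlation 0.3: SE 0.0579 gives 0.98 to 1.23. SE 0.0533 gives 0.99 to 1.22.

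**Detection.** In Set A with fading and an assumed shift of 0.067 SD (true ratio 1.08-1.14), the 95% interval excluded 1 in 53-81% of trials without the term and 69-89% with it.

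**First occurrences only.** The SE ratio was 0.73-0.97 in Set A and 0.77-1.03 in Set B. The ratio itself also moved. In Set B with 3% events, correlation 0.6 and ICC 0.01, it was 1.21 unadjusted and 1.28 adjusted, while the SE rose from 0.0738 to 0.0759. The two ratios estimate different quantities.

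**Missing entry values.** With half missing (Set A, 13% share), the cut is 4-11% with fading and 11-18% without.

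**Entry draws taken too late.** With a true ratio of 1.19 and every entry draw already carrying the whole effect, the adjusted ratio is 1.12-1.17 (fading) or 1.05-1.13 (not). In Set B, 1.185 fell to 1.139 when half the effect was present at entry and to 1.091 when all of it was.

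**The case against.** The strongest reply is that nothing here is an error. Unadjusted safety rates are conventional, no power target is missed, and with the unadjusted ratio kept as the main result its interval does not change. That stands: this is an optional gain, and the higher detection figures belong to the companion ratio only. The hospitalization GEE names no covariates either. Laboratory events differ in that the same quantity is measured monthly and could be available at entry.

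The second reply concerns feasibility. The documents do not show that laboratory values from before the first transferred session are in the data. The KDQOL window reaches back 90 days, but it concerns another instrument. Nor do they say that the first transferred session is the first under the facility's assignment, so even an early value could follow some exposure. Both limits stand.

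The third reply is that adjustment could hide harm if entry values are drawn late. The figures above confirm this. It is why the unadjusted ratio must remain the main one and why the KDQOL window, which runs to 120 days after the first session, should not be copied.

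A reader might go further and infer bias, because "the randomized treatment assignment for the dialysis facility will be determined before patients are enrolled". The documents show no entry difference between arms. The chance standard error of the entry mean difference is about sqrt(4/6880 × (1 + 25.9 × 0.02)) = 0.030 SD at an assumed ICC of 0.02. Even an assumed 0.067 SD deficit with no treatment effect gives a ratio of only 1.03-1.06 without the term and 1.01-1.04 with it (fading, 13% share). One entry value would therefore remove only part of such a difference.

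**Conclusion.** The point holds as a loss of precision, conditional on the counting rule. With repeated monthly events counted, leaving out the entry value makes the standard error of each laboratory log rate ratio larger than it need be. Adding the value would cut it by roughly 5-40% over the assumed range, and by about 7-23% if within-patient correlation fades.

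It is tempting to say that the gain exists whatever is counted. It does not: with first occurrences only it is smaller and can vanish, and the adjusted and unadjusted ratios should not then be compared directly. Nor do the documents support reading this as an invalid safety comparison or as a threat to the primary mortality result.

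The sizes rest on assumed correlations, event shares and ICC, and on usable pre-session laboratory values being in the transfer. Confidence in the direction is good for repeated events; confidence in the size is moderate.

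**What to change.** In SAP 4.5.3:

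1. State that repeated monthly events are counted, and keep the planned unadjusted rate ratio as the main safety comparison.
2. Beside it, for potassium, phosphorus, bicarbonate and albumin, report the same GEE with that analyte's entry value as a continuous covariate.
3. Define the entry value as the last value up to and including the first transferred session. Use a missing-value indicator for patients with none, and do not count the entry value as an event in that model.
4. Allow a draw within 14 days after the first session only in a supplementary version, since later draws can absorb part of the effect.
5. State that a signal in the unadjusted ratio is not dismissed because the adjusted one is smaller.

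The cost is SAP wording, one derived variable per analyte and some extra model fits. Four analytes in the three populations of SAP 4.5 make 12 fits, or 24 with the supplementary version, before any stratified analyses. No new data are collected. The share of patients with a pre-session value should be tabulated first; if it is small, the gain will be small too.
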